16.2.2 Secondary Outcome Measures

Measured reductions in cocaine and other drug use

- **A.** The proportion of successful subjects. A successful subject is one who reduces the overall proportion of cocaine use days to 75% or less of his/her baseline rate.
- **B.** The proportion of successful subjects. A successful subject is one who reduces the overall proportion of cocaine use days to 50% or less of his/her baseline rate.
- **C.** The proportion of successful subjects. A successful subject is one who reduces use days to 75% of his/her baseline level according to subject self report without regard to BE levels.
- **D.** Weekly proportion of non-use days according to subject self report without regard to BE levels.

- **E.** Weekly proportion of non-use days of other drug use, by other drug according to both SUR and urine toxicology results.
- **F.** Weekly mean urine BE level.
- **G.** Proportion of cocaine non-use days during the 8 week treatment period (non-use days divided by non-missing study days)
- **H.** The maximum number of consecutive cocaine non-use days.

Reduction in the severity of cocaine dependence and craving

- I. CGI-O scores.
- J. CGI-S scores.
- **K.** ASI scores.
- L. BSCS scores.

Severity of depression

M. HAM-D scores.

Safety of STS

AEs, laboratory data, physical exams, and vital signs.

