TREATMENT COMPLIANCE: Treatment compliance will be determined by investigative staff recording patch use at each visit and assessing blood levels of selegiline/selegiline metabolites. Analysis of selegiline, N-desmethylselegiline, L-amphetamine, and L-methamphetamine plasma concentration will be determined at screening and after 2 and 5 weeks of treatment by a central laboratory to maintain the study blind.

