The rationale for using the transdermal patch in lieu of the IR oral capsule is due to possible favorable differences in the pharmacokinetic and metabolic profiles. Compared to the oral capsule, the STS provides a continuous release of selegiline over a 24-hour period and avoids first-pass metabolism allowing for higher and more sustained plasma levels of selegiline, while reducing the levels of the main metabolites, R(-)-N-desmethylselgiline, R(-)-amphetamine, and R(-)-methamphetamine. Transdermal delivery of selegiline also minimizes direct, high concentration contact with the MAO system of the gut and liver, reducing the probability for drug and food interactions, most notably tyramine. The STS 20 mg/20 cm² dose was chosen for study in the present trial based on data supporting the safety and efficacy in depression and the positive results of tyramine interaction studies (see below).

Somerset Pharmaceuticals, Inc. has performed numerous studies to evaluate the tyramine sensitivity of subjects administered the selegiline transdermal system (STS) and has subsequently eliminated dietary tyramine restrictions normally associated with MAO inhibitor treatment from all clinical study protocols involving the STS. Tyramine challenge studies evaluate the potential of tyramine-induced hypertensive episodes secondary to treatment with MAO inhibitors under controlled clinical conditions. An increase in systolic blood pressure (SBP) of > 30 mm Hg above a baseline value is typically used to define tyramine sensitivity.

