14.2 ASSESSMENTS DURING DOUBLE-BLIND TREATMENT

Over the 8-week period of active treatment, subjects will return to the clinic three times per week (ideally on Monday, Wednesday, and Friday). Assessments will be performed as follows:

At each visit:

- 1. SUR
- 2. Urine BE and creatinine
- 3. Vital signs (just the first two weeks then weekly thereafter)
- 4. Treatment compliance-drugs
- 5. Treatment compliance-therapy (at each session attended)

Once per week at the first visit each week:

- 1. Vital signs (after the first two weeks when vital signs are taken at each visit)
- 2. Urine drug screen
- 3. AEs
- 4. Concomitant medications
- 5. BSCS
- 6. CGI-S
- 7. CGI-O

At the first visit of weeks 3 and 6:

1. Blood for selegiline/selegiline metabolites

At the first visit of study week 4:

- 1. Hematology
- 2. Blood chemistries
- 3. Routine urinalysis
- 4. Pregnancy test (if female)

At the first visit of study weeks 3, 5, and 7

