14.6.12 Urine Drug Screen (Qualitative Analysis of Substances of Abuse)

The first sample of each week taken for BE and creatinine analysis will be analyzed additionally for amphetamines, barbiturates, benzodiazepines, and opiates and each time during screening.

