14.6.13 Self Report of Use (SUR)

The SUR includes the subject's daily report of use of cocaine, alcohol, marijuana, opioids, and nicotine since the last clinic visit.

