14.6.22 Blood Selegiline/Selegiline Metabolite Levels

Analysis of selegiline, N-desmethylselegiline, L-amphetamine, and L-methamphetamine plasma concentration will be determined during screening and after 2 and 5 weeks of treatment. Blood should be collected prior to the first dose and within 15 minutes prior to the application of new patches during weeks 3 and 6. The analysis will be performed by the University of Utah, Center for Human Toxicology using a validated liquid chromatography atmospheric pressure chemical ionization tandem mass spectrometry measurement. The procedure for blood collection, storage, and shipping is provided in Appendix IV.

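### Secondary outcome E does not fit its data sources: only opioids have both self-report and urine results, and if urine alone may count, the amphetamine category can be biased against STS

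*Protocol*

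**What the plan says.** Outcome E in section 16.2.2 is "Weekly proportion of non-use days of other drug use, by other drug according to both SUR and urine toxicology results". No drug class is excluded. Section 16.4 compares E between arms by GEE, and the secondary objectives in sections 5 and 16.1 include reductions in the use of other drugs.

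The two sources are described separately. Under section 14.6.12, the first weekly specimen "will be analyzed additionally for amphetamines, barbiturates, benzodiazepines, and opiates". Section 14.2 lists the drug screen among the assessments done "Once per week at the first visit each week". Under section 14.6.13, the SUR is the subject's "daily report of use of cocaine, alcohol, marijuana, opioids, and nicotine since the last clinic visit".

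On the study drug, section 4 describes the patch, compared with the oral capsule, as "reducing the levels of the main metabolites, R(-)-N-desmethylselgiline, R(-)-amphetamine, and R(-)-methamphetamine". Section 14.6.22 adds: "Analysis of selegiline, N-desmethylselegiline, L-amphetamine, and L-methamphetamine plasma concentration will be determined during screening and after 2 and 5 weeks of treatment". The synopsis has this plasma assay done "by a central laboratory to maintain the study blind".

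**The concern.** E asks for one thing, a per-drug weekly proportion of non-use days resting on self-report and urine together. The two instruments that feed it cover almost entirely different drugs. How E turns out then depends on how the word *both* is read, and the text does not settle that.

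The amphetamine class needs particular care. It is on the urine panel, it is not on the self-report, and amphetamine and methamphetamine are products of the active treatment. Placebo patches cannot produce them. If urine alone is allowed to score use, any positive caused by metabolites arises in the STS arm only. It would look like stimulant use on STS, both against placebo and against the subject's own drug-free baseline. A stated secondary objective would then carry a difference created by the measurement.

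**Working it through.** The protocol gives no figure for E, so there is none to reproduce. The check sets the two source lists side by side and then asks what follows under each reading.

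**Step 1: coverage** (SUR from section 14.6.13, urine panel from section 14.6.12, cocaine left out).

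| Substance | SUR | Urine screen |
|---|---|---|
| Opioids/opiates | yes | yes |
| Alcohol | yes | no |
| Marijuana | yes | no |
| Nicotine | yes | no |
| Amphetamines | no | yes |
| Barbiturates | no | yes |
| Benzodiazepines | no | yes |

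That is 4 + 4 − 1 = 7 substances, of which 1 has both sources and 7 − 1 = 6 have one. Even the single overlap is not stated consistently at baseline: section 13.2 lists opiates in the baseline SUR and section 14.1.2 omits them.

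**Step 2: if both sources are required.** E can be computed for opioids only. Amphetamines have no self-report, so E has no amphetamine result, and no false excess can arise from it.

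**Step 3: if either source suffices.** All seven substances can be scored, and an amphetamine-positive screen counts as use. Let p0 be the background positive rate in both arms, and f the share of otherwise negative STS screens made positive by metabolites. With no true difference in drug use,

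p_STS = p0 + (1 − p0) × f.

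Neither p0 nor f is in the protocol, so the values below are assumptions. For illustration, take one screen per subject, n = 150 per arm (section 3), and a two-sided 5% test (section 16.4):

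power = Φ{ [ (p_STS − p0) − 1.96 × √(2p̄(1 − p̄)/n) ] / √[ (p0(1 − p0) + p_STS(1 − p_STS))/n ] }, where p̄ is the mean of the two rates.

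Example with p0 = 5% and f = 5%: p_STS = 0.05 + 0.95 × 0.05 = 0.0975. The two standard errors are 0.0302 and 0.0301, so (0.0475 − 1.96 × 0.0302)/0.0301 = −0.39, which gives 35%.

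Chance of a significant false excess on STS:

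| f | p0 = 2% | p0 = 5% | p0 = 10% |
|---|---|---|---|
| 2% | 17% | 10% | 7% |
| 5% | 54% | 35% | 22% |
| 10% | 92% | 80% | 60% |
| 20% | 100% (rounded) | 99.8% | 98% |

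At f = 0, as with an assay that ignores the metabolites, the arms have the same rate and there is no bias.

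**Step 4: the unit.** E counts days, but a urine-only class has one specimen a week. The day-scoring rules in section 16.2.1 concern cocaine and BE only. If their one-day logic were borrowed, a positive screen would turn one day of seven into a use day. The weekly value could then be only 7/7 = 100% or 6/7 = 85.7%, with the other days counted as non-use on no evidence. On that scale, at p0 = 5%, the metabolite effect (p_STS − p0)/7 would be 0.0475/7 = 0.7 points at f = 5%, 0.19/7 = 2.7 points at f = 20%, and 0.95/7 = 13.6 points at f = 100%.

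**The case against.** The strongest counter-argument is that the two defects do not combine. A reader might infer that the lack of overlap is what produces a false excess of drug use on STS, or that E as written will count exposure to treatment as stimulant use. The protocol supports neither. Requiring both sources removes amphetamines from E. The excess needs the other reading, and the text does not choose between them. Even then, a non-specific screen turns positive only above its cut-off. The protocol gives no cut-off, cross-reactivity or urine metabolite level, and it says that the patch lowers these metabolites relative to the oral capsule. A false-positive share near 100% therefore has no support in the document. The probabilities in the second table rest wholly on assumed inputs and on a simpler test than the planned GEE. All of this stands.

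It can also be said that scoring rules and assay details belong in an SAP or laboratory manual, and that section 16.4 allows for adjustments. This stands in part. However, the panel, the SUR content, the weekly frequency and the definition of E are fixed in the protocol, and no later document can supply self-report that was never collected. Reading E as using whichever source covers each drug is sensible, but it is the reading that lets amphetamine positives count.

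A reader might further infer that the screen would unblind the sites. Section 14.6.11 already withholds central urine results from sites and bars local analysis of the samples, and the drug screen uses those same specimens during treatment.

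Finally, the consequence is limited. E is one of 13 lettered secondary measures (A to M), it is reported drug by drug, and any bias runs against STS. That stands too.

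**Conclusion.** The point holds as a mismatch between E and its data, with a conditional bias in one category. What is certain from the text is that six of the seven non-cocaine substances lack one of the two sources, and that the three urine-only classes cannot yield a proportion of days from one specimen a week. What is conditional is the bias against STS in the amphetamine category. It requires that urine alone may score use and that the assay detects selegiline metabolites above its cut-off. Its size cannot be taken from the protocol and may be zero. If those conditions hold, a small metabolite-caused share would be enough to matter: under the single-screen illustration, 10% gives a 60% to 92% chance of a significant false difference for assumed background rates of 10% down to 2%. The primary outcome, based on cocaine self-report and BE, is not affected. This should be corrected, but it does not threaten the trial's main conclusion.

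**What to change.** Define E by source:

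- **Alcohol, marijuana and nicotine:** weekly proportion of non-use days from the daily SUR.
- **Opioids:** SUR plus urine, with a stated rule for combining them, and with the baseline SUR lists in sections 13.2 and 14.1.2 reconciled.
- **Barbiturates and benzodiazepines:** proportion of weekly specimens positive, not a proportion of days.
- **Amphetamines:** leave on-treatment results out of the between-arm comparison in E unless the assay is shown to separate selegiline metabolites from other amphetamine sources. Otherwise report them descriptively, with that caveat.

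The cost is the redefinition of one secondary outcome, with no new visit, form or assay. If the assay is not specific, the trial gives up an on-treatment comparison of amphetamine use. That is a real loss, since amphetamines are among the medications section 13.13 says not to use during treatment. Establishing the assay's specificity and cut-off first would show whether that loss is necessary.

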16.3 INTENT-TO-TREAT AND EVALUABLE POPULATIONS

The intent-to-treat population is defined as the subjects who are randomized to treatment. The evaluable population is defined as the subjects who are properly qualified to participate in the study in accordance with the inclusion and exclusion criteria and who contribute at least four (4) usable on-study urine samples and 21 days of self report.

16.4 ANALYSIS PLAN

Each of the primary and secondary efficacy outcome measures will be analyzed for the intent-totreat and for the evaluable population. Major differences in the results, if any, will be further explored. While there is every intent to be complete in describing the analyses to be performed, it is not possible to anticipate every contingency and some adjustments may be required to meet constraints posed by the structure of the data.

All statistical tests will be two-sided at a 5% level of alpha. Confidence intervals will be two-sided with a 95% confidence coefficient.

Primary Efficacy Outcome

The primary outcome variable for each subject is the weekly proportion of cocaine non-use days. Each subject's weekly proportion is equal to the number of his/her cocaine non-use days divided by the number of his/her non-missing study days during that week (a maximum of 6 days for week 1 and 7 days for weeks 2 through 8).

The weekly mean proportion of cocaine non-use days on study will be compared between treatment groups using Generalized Estimating Equations (GEE). GEE provide a model-based regression methodology applicable for the analysis of the correlated data that will result from this repeated measures longitudinal study.

The GEE procedure proposed by Liang and Zeger¹⁸ and Zeger and Liang¹⁹ (Biometrics, 1986) model the population average and has several useful features:

- 1. It can be used to analyze different types of outcomes such as continuous, binary, or count.
- 2. It can be used to analyze an unbalanced design caused by either differing numbers of observations per person or by observations taken at different times.
- *3.* The parameter estimates are consistent even if assumptions about the variance structure are not completely accurate.

Secondary Efficacy Outcomes

As a secondary analysis, the baseline proportion of cocaine non-use days, site, gender, diagnosis of ADD, severity of depression during screening, and their first-order interactions with treatment will also be included in the model. Presentation will include the full model with all terms and a reduced model containing only significant terms.

Unless the primary response analysis implies the need for a more elaborate model, between group comparisons of the secondary outcomes will be performed as follows:

- 1. Proportion of successful subjects, measures A, B, and C, will be assessed by Chi-square tests.
- 2. Weekly mean proportion of cocaine non-use days, other drug non-use days, BE levels measures D, E, and F, by GEE.
- 3. The proportion of cocaine non-use days on study and the maximum number of consecutive cocaine non-use days and proportion of cocaine non-use days, measures G and H, will be assessed by t-test.
- 4. Weekly CGI-self, CGI-observer, and BSCS, monthly ASI, and biweekly HAM-D score, measures I, J, K, L, and M, will be assessed by GEE.
- 5. Adverse events, laboratory data, physical exams, and vital signs will be reported in tabular form. AEs will be listed indicating the frequency of each type of event by various demographic characteristics such as gender, ethnicity, age, duration of addiction, other

medical problems both related to and independent of the addiction, and combinations of these characteristics. The frequencies of adverse events by type will be compared between study arms using Chi-square analyses.

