10.3 ADAPTIVE RANDOMIZATION

Adaptive random allocation of subjects to study groups was developed to balance groups with respect to screening prognostic variables. The procedure allocates treatment assignment based on the assignments and prognostic variable levels for all previously enrolled subjects. The treatment groups will be balanced with respect to gender, diagnosis of ADD, historical Self-Report of cocaine use (< 18 or \ge 18 days of use in the last 30 days), and severity of depression (HAM-D score \le 11 or > 11). A new subject will be randomized with a "biased coin" procedure which uses randomization probabilities, favoring the treatment with the deficit enrollment, to improve the balance on group assignment.¹⁰ The randomization process will be performed by computer at CSPCC.

Rationale for ADD as a stratification variable. It has been observed that a relatively high percentage of cocaine abusing or dependent individuals have a current diagnosis of ADD or a past history of ADHD. For example, in one sample of 281 cocaine abusers seeking treatment, 12% of the individuals met DSM-IV criteria for childhood ADHD, and 10% for adult ADD.¹¹ In another report, 35% of 298 treatment-seeking cocaine abusers met DSM-III-R criteria for childhood ADHD.¹² Compared to those who did not have a childhood ADHD diagnosis, those that did, reported more severe substance use, earlier onset of cocaine abuse, and more frequent and intense cocaine use. Other studies assessing the prevalence of ADD in individuals seeking treatment for cocaine abuse or dependence, as well as those assessing the prevalence of cocaine use in subjects seeking treatment for ADD, and evaluating the adult status of children who were treated for ADHD, support the association between ADD and cocaine use. It is possible that cocaine use by some individuals with ADD/ADHD may be an attempt to self-medicate for the disorder. Given the association between ADD/ADHD and cocaine use, as well as preliminary data indicating that selegiline may be effective for the treatment of ADD/ADHD, it is appropriate to balance groups in the present study with respect to a diagnosis of ADD. Individuals who are identified as having ADD as part of the study screening process will be informed of this, and will be encouraged to seek further evaluation and appropriate treatment.

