16.6 SAMPLE SIZE ESTIMATE

The proposed primary outcome measure is the weekly proportion of cocaine non-use days. Power analyses were made based on assumptions of normal distribution, equal correlation between observations at any two times (exchangeable) working correlation and a common standard deviation of 33.5%. These assumptions are based on preliminary results of an eightweek selegiline study (Protocol Number: CS-1017), in which an oral dose of selegiline was compared to placebo in cocaine dependent subjects. We further make the assumption that a 10% increase in the proportion of cocaine non-use days of the STS treatment group over the placebo group would be considered clinically significant. Based on the sample size calculation for GEE procedures proposed by Liu and Liang²⁰, then 110 subjects will be required in each arm to detect this clinically meaningful difference with a power of 80% at the 0.05 level of significance. The retention rates in studies of cocaine addicts currently being conducted by NIDA are approximately 70%, therefore at least 150 subjects should be randomized into each treatment to ensure an adequate sample size at the end of the trial.

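### The primary GEE is unadjusted for baseline cocaine use and the four randomization factors: valid, but conservative and less powerful to the extent that these variables are prognostic

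*Protocol*

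**What the plan says.** Under Primary Efficacy Outcome, Protocol 16.4 gives the confirmatory comparison: "The weekly mean proportion of cocaine non-use days on study will be compared between treatment groups using Generalized Estimating Equations (GEE"). No covariate is named.

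Covariates appear under Secondary Efficacy Outcomes: "As a secondary analysis, the baseline proportion of cocaine non-use days, site, gender, diagnosis of ADD, severity of depression during screening", each with its first-order interaction with treatment. Results are to be shown for a full model and for a reduced model that keeps only significant terms.

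Protocol 10.3 uses a biased coin: "The treatment groups will be balanced with respect to gender, diagnosis of ADD, historical Self-Report of cocaine use" (cut at 18 of the last 30 days) and HAM-D severity. Both 10.3 and 16.7 describe these as prognostic variables. The 30-day use factor is not in the covariate list of 16.4.

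Sections 13.2 and 14.1.2 require a 14-day baseline with six urine specimens and daily self-report, so baseline use is known for every randomized subject.

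For planning, 16.4 states "All statistical tests will be two-sided at a 5% level of alpha". Section 16.6 powers the trial for a "10% increase in the proportion of cocaine non-use days of the STS treatment group over the placebo group", "with a power of 80% at the 0.05 level of significance", and mentions no covariate adjustment.

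**The concern.** The design and the analysis treat the same variables differently. Allocation is steered to balance four factors because they are thought to predict outcome. The unadjusted variance then counts their contribution as noise that could have fallen unevenly between arms, although the allocation has largely prevented that. If the factors do predict outcome, the reported standard error exceeds the true sampling variability, and the test rejects less often than its nominal level under the null.

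Separately, leaving out the baseline proportion of non-use days gives up whatever precision that measurement would bring. What is at stake is power and the width of the confidence interval for the treatment difference. Protection against a false positive is not at stake.

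The secondary model does not fill the gap. With treatment interactions for every covariate, including about 16 sites, and a reduction step driven by significance, it yields no single adjusted treatment effect fixed in advance. It also lacks one of the four balancing factors.

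**Working it through.** **Inputs from the protocol.** Two-sided alpha 0.05 (16.4); power 80%, difference 10 and "a common standard deviation of 33.5", both read as percentage points (16.6); 8 weekly proportions per subject (16.4); "equal correlation between observations at any two times (exchangeable) working correlation" (16.6); 110 per arm needed and 150 per arm randomized (16.6); final test at 0.044 (16.8).

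**Not in the protocol, so assumed over a range.** The exchangeable correlation rho, the correlation between baseline and treatment weeks, and the share of variance explained by the balancing factors.

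**Step 1: reproduce 110 per arm.** For a continuous outcome with exchangeable correlation,

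n per arm = 2 × (1.96 + 0.8416)² × 33.5² / 10² × (1 + 7 rho)/8 = 176.2 × (1 + 7 rho)/8.

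Setting n = 110 gives rho = 0.571. Nearby values give 100 (rho 0.50), 107 (0.55) and 115 (0.60). The figure is consistent with the named method but cannot be confirmed, because rho is not stated. The implied SD of a subject's 8-week mean is 33.5 × √0.624 = 26.5, and the standard error of the difference is 26.5 × √(2/110) = 3.57.

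**Step 2: variance explained by baseline.** Let r be the correlation between any baseline week and any treatment week, with two baseline weeks that share the same rho. Then

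R² = r² / [((1 + rho)/2) × ((1 + 7 rho)/8)] = r² / (0.785 × 0.624) = r² / 0.490.

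This gives R² = 8%, 17% and 33% for r = 0.20, 0.285 and 0.40.

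**Step 3: power.** Adjustment multiplies the standard error by √(1 − R²). Power = Φ(10/SE − z), with z = 1.96 for alpha 0.05 and 2.01 for 0.044. The 0.044 column is a fixed-sample calculation that ignores the interim look.

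| r (assumed) | R² | 110 per arm, 0.05 | 110 per arm, 0.044 | 150 per arm, all contributing fully, 0.05 |
|---|---|---|---|---|
| 0 | 0 | 80% | 78% | 91% |
| 0.20 | 8% | 83% | 82% | 93% |
| 0.285 | 17% | 87% | 85% | 95% |
| 0.40 | 33% | 93% | 92% | 98% |

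Before rounding, the gains at alpha 0.05 are about 3, 7 and 13 points at 110 per arm, and about 2, 4 and 7 points at 150 per arm.

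**Step 4: size of the unadjusted test.** If the balanced factors explain a share R² of the variance and are perfectly balanced, the true size is 2 × [1 − Φ(1.96/√(1 − R²))]. For R² = 2%, 5%, 10% and 20% this is 4.8%, 4.4%, 3.9% and 2.8%. A biased coin improves balance without making it perfect, so for each assumed R² these are the lowest sizes possible.

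**Step 5: simulation check.** There were 1,500 runs per setting, with 220 subjects, a coin probability of 2/3 applied to the margins of four binary factors, subject means and robust standard errors. Here r is the correlation of baseline with the subject's mean outcome. Factor R² is the share due to gender, ADD and HAM-D; historical use was made to depend on baseline.

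| Factor R², r (assumed) | Null rejection, unadjusted / adjusted | Power at 10 points, unadjusted / adjusted |
|---|---|---|
| 0, 0 | 4.7% / 5.0% | 80.9% / 80.3% |
| 0.05, 0.3 | 4.1% / 4.8% | 79.9% / 84.7% |
| 0.05, 0.5 | 3.5% / 5.0% | 80.0% / 90.9% |

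In the last setting under the null, the unadjusted mean standard error was 3.57 against a true SD of 3.27; adjusted, it was 2.99 against 2.98. The Monte Carlo error of a 5% rejection rate is √(0.05 × 0.95/1500), about 0.6 points. The 4.1% alone is therefore not clearly below 5%, whereas the 3.5% is.

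**The case against.** The strongest reply is that nothing here is invalid. An unadjusted comparison of randomized groups is unbiased, it errs on the conservative side, and adjusted results will be reported in any case. That stands. A reader might infer from the missing covariates that the primary result would be biased, or that its false-positive rate would exceed 5%. The protocol supports neither inference.

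A reader might also take it as settled that the standard error is too large and the test under-sized. That goes beyond the document, which gives neither rho, nor a baseline-to-outcome correlation, nor any variance share for the balancing factors. With non-prognostic covariates the two analyses perform alike. The protocol asserts that the balancing factors are prognostic but does not say how strongly.

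Three further objections limit the size:

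- Entry requires at least three positive urine specimens during baseline (9.1). This may narrow the range of baseline non-use and weaken its correlation with outcome.
- The intent-to-treat population is all 150 per arm, and GEE can use partial data from dropouts, so 110 per arm overstates the gain if most subjects contribute.
- The baseline proportion of non-use days is a close proxy for 30-day historical use, so omitting the latter from the secondary model is a small fault.

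It could also be said that covariates belong in the SAP. That does not answer the point, because the protocol itself places adjustment outside the primary analysis.

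**Conclusion.** The concern holds as a loss of efficiency that depends on how prognostic the variables are. Protocol 16.4 fixes an unadjusted primary test although the trial balances on four factors that it calls prognostic and measures baseline use on everyone.

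The power gain forgone is about 3 to 13 points at 110 per arm and alpha 0.05, or about 2 to 7 points if all 150 per arm contribute fully. Both ranges assume baseline-to-treatment-week correlations of 0.20 to 0.40 and the rho of 0.57 implied by the sample size; the gain is zero at zero correlation. The 4.4%, 3.9% and 2.8% sizes are lower bounds for assumed factor shares of 5%, 10% and 20%.

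The direction is well supported; the size is not known from the protocol. The change should be made because it costs almost nothing, but the trial is not invalid without it.

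**What to change.** In 16.4, state that the primary GEE uses an identity link, so that the estimate stays a difference in mean proportion of non-use days, the scale on which 16.6 is planned. State that it includes treatment, week, baseline proportion of non-use days, gender, ADD, historical-use stratum and HAM-D severity as main effects. Name the adjusted difference as the primary estimate and keep the unadjusted comparison as a sensitivity analysis. Add historical use to the secondary covariate model.

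Before a HAM-D stratum can be used, its definition must be reconciled: 10.3 splits at ≤ 11 versus > 11, while 16.7 splits at ≥ 11 versus < 11, so a score of exactly 11 falls on different sides. Entering HAM-D as a continuous score avoids dependence on the cut in the model, though the two sections should still agree.

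The cost is a few sentences in the protocol, settled before unblinding. Every covariate is already collected before randomization, so no subjects, visits or assessments are added.
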